4.2. Inclusion Criteria

Subjects must meet all of the following inclusion criteria to be eligible for participation in this study.

- 1) Willing and able to give informed consent prior to any study-specific procedures being performed
- 2) Males and nonpregnant, nonlactating females equal to or greater than 18 years of age; inclusive based on date of the Screening visit
- 3) Diagnosis of PSC based on cholangiogram (MRCP, endoscopic retrograde cholangiopancreatography [ERCP], or percutaneous transhepatic cholangiogram [PTC]) or liver biopsy
- 4) Subjects have evidence of cirrhosis based on at least one of the three following criteria
 - a) Historical liver biopsy that reveals Ludwig stage F4 fibrosis (or equivalent)
 - b) Abdominal imaging with features consistent with cirrhosis in the opinion of the investigator (eg, small nodular liver, splenomegaly, evidence of portosystemic collaterals, diffuse surface irregularity). magnetic resonance imaging (MRI), computed tomography (CT), and/or ultrasound are acceptable modalities to make this determination.
 - c) Any one of the following completed at Screening visit:
 - i) FibroScan \geq 14.4 kPA
 - ii) ELF \geq 11.3
 - iii) FibroTest \geq 0.75

- 5) Subject has the following laboratory parameters at the Screening visit, as determined by the central laboratory:
 - a) Estimated glomerular filtration rate (eGFR) > 60 mL/min, as calculated by the Cockcroft-Gault equation
 - b) ALT $\leq 5 \times$ ULN
 - c) Total bilirubin ≤ 2 mg/dL, unless the subject is known to have Gilbert's syndrome or hemolytic anemia
 - d) INR ≤ 1.4 , unless due to therapeutic anticoagulation
 - e) Platelet count $\geq 75,000/\mu\text{L}$. Patients with evidence of high-risk esophageal or gastric varices in the opinion of the investigator are excluded
 - f) Negative anti-mitochondrial antibody
- 6) For subjects on UDCA, the dose of UDCA must have been stable in the opinion of the investigator for at least 6 months before screening. For subjects not on UDCA, no UDCA use for at least 6 months prior to screening.
- 7) For subjects being administered biologic treatments (eg, anti-tumor necrosis factor or anti-integrin monoclonal antibodies), immunosuppressants, or systemic corticosteroids, the dose must have been stable in the opinion of the investigator for at least 3 months prior to screening and anticipated to remain stable throughout the study.

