4.3. Exclusion Criteria

Subjects who meet *any* of the following exclusion criteria are not to be enrolled in this study.

- 1) Current or prior history of any of the following
 - a) Decompensated liver disease, including ascites, hepatic encephalopathy (HE), or variceal hemorrhage

- b) Liver transplantation
- c) Cholangiocarcinoma or hepatocellular carcinoma (HCC). If a dominant structure has been identified, cholangiocarcinoma must be adequately excluded in the opinion of the investigator prior to Day 1
- 2) Model for end-stage liver disease (MELD) score > 12 at screening, unless due to an alternate etiology such as therapeutic anticoagulation
- 3) CP score > 6 at screening, unless due to an alternative etiology such as Gilbert's syndrome or therapeutic anticoagulation
- 4) Presence of moderate to severe itch in the opinion of the investigator at screening and Baseline/Day 1
- 5) Ascending cholangitis within 30 days of screening
- 6) Presence of a percutaneous drain or biliary stent
- 7) Other causes of liver disease including IgG4-related sclerosing cholangitis, PSC-autoimmune hepatitis overlap syndrome, secondary sclerosing cholangitis, and viral, metabolic, alcoholic, and other autoimmune conditions. Subjects with hepatic steatosis may be included if there is no evidence of NASH in the opinion of the investigator.
- 8) Current moderate to severely active IBD (including ulcerative colitis, Crohn's disease, and indeterminate colitis). See Section [6.8.6](#).

Note: Subjects with IBD who currently have an external ostomy bag and/or proctocolectomy are not subject to this exclusion criterion and need not undergo IBD Symptom Severity Assessment.

- 9) Current or prior history of any of the following:
 - a) Malignancy within 5 years of screening with the following exceptions:
 - i) Adequately treated carcinoma in situ of the cervix
 - ii) Adequately treated basal or squamous cell cancer or other localized nonmelanoma skin cancer.

Subjects under evaluation for possible malignancy are not eligible.

- b) Unstable cardiovascular disease as defined by any of the following:
 - i) Unstable angina, myocardial infarction, coronary artery bypass graft surgery or coronary angioplasty within 6 months prior to screening
 - ii) Transient ischemic attack or cerebrovascular accident within 6 months prior to screening

- iii) Symptomatic obstructive valvular heart disease or hypertrophic cardiomyopathy
- iv) Symptomatic congestive heart failure

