5.4. Prior and Concomitant Medications

Concomitant use of certain medications or herbal/natural supplements with study drug may result in PK and/or PD interactions resulting in increases or decreases in exposure of study drug(s) or these medications.

Concomitant medications taken within 28 days of screening through the follow-up visit need to be recorded in the source documents and electronic case report forms (eCRFs).

CILO increased atorvastatin exposure (39%) which does not necessitate a priori dose modification based on the LIPITOR United States prescribing information (USPI). Subjects taking atorvastatin with CILO should be monitored as per label recommendations.

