6.8.5. Clinical Liver Assessments

The MELD and CP scores will be calculated from the central laboratory values attained at each visit. CP will be calculated by the site at screening to assess eligibility; MELD may also be calculated by the sites at screening to determine eligibility if the central laboratory is unable to perform the calculation. MELD will be monitored by site at each visit for safety. Assessment of ascites and HE will be determined by the site at all visits as in the [Table 6-1](#) and will be entered into the eCRF. Dialysis in the preceding week will also be determined by the site at each visit. HE will also be assessed using the West Haven Criteria ([Appendix 5](#)).

Table 6-1. Child-Pugh (CP) Classification of the severity of cirrhosis

| | 1 | 2 | 3 |
|-----------------------------|--|--|---|
| Hepatic Encephalopathy (HE) | None No encephalopathy and not on any treatment for hepatic encephalopathy | Medication-Controlled Subject is lethargic, may have moderate confusion Subject is receiving medical therapy for HE | Medication-Refactory Marked confusion/incoherent, rousable but sleeping or comatose |
| Ascites | None No ascites and not on treatment for ascites | Mild/Moderate Cross sectional imaging showing ascites Abdominal distension Medication for ascites | Severe (diuretic-refractory) Visible clinically |
| Bilirubin (mg/dL) | < 2 | 2-3 | > 3 |
| Albumin (g/dL) | > 3.5 | 2.8-3.5 | < 2.8 |
| INR | < 1.7 | 1.7-2.3 | > 2.3 |

CP score is obtained by adding the score for each parameter.

CP class: A 5-6 points
 B 7-9 points
 C 10-15 points

The MELD score will be calculated by using the following formula:

$$10 \times ((0.378 \times \ln (\text{Total Bilirubin (mg/dL)})) + (1.12 \times \ln (\text{INR})) + (0.957 \times \ln (\text{Serum Creatinine (mg/dL)})) + 0.643).$$

Serum creatinine in $\mu\text{mol/L}$ will be converted to mg/dL by multiplying by 0.01131. Total bilirubin in $\mu\text{mol/L}$ will be converted to mg/dL by multiplying by 0.05848. Round total bilirubin to 1 decimal place and serum creatinine to 2 decimal places prior to using values in formula or calculation criteria.

[figure not shown]

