4.3. Protocol Deviations

A by-subject listing will be provided for those subjects who did not meet at least 1 eligibility (inclusion or exclusion) criterion. The listing will present the eligibility criterion (or criteria if more than 1 deviation) that subjects did not meet and related comments, if collected.

Protocol deviations occurring after subjects entered the study are documented during routine monitoring. A by-subject listing will be provided for those subjects with important protocol deviation.

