Appendix 2. CTCAE Grade for Laboratory Parameters

CTCAE 5.0	CTCAE Grade				
CTCAE Term	Grade 1	Grade 2	Grade 3	Grade 4	Grade 5
Anemia	Hemoglobin (Hgb) <LLN - 10.0 g/dL; <LLN - 6.2 mmol/L; <LLN - 100 g/L	Hgb <10.0 - 8.0 g/dL; <6.2 - 4.9 mmol/L; <100 - 80g/L	Hgb <8.0 g/dL; <4.9 mmol/L; <80 g/L; transfusion indicated	Life-threatening consequences; urgent intervention indicated	Death
Activated partial thromboplastin time prolonged	>ULN - 1.5 x ULN	>1.5 - 2.5 x ULN	>2.5 x ULN; bleeding	-	-
Alanine aminotransferase increased	>ULN - 3.0 x ULN if baseline was normal; 1.5 - 3.0 x baseline if baseline was abnormal	>3.0 - 5.0 x ULN if baseline was normal; >3.0 - 5.0 x baseline if baseline was abnormal	>5.0 - 20.0 x ULN if baseline was normal; >5.0 - 20.0 x baseline if baseline was abnormal	>20.0 x ULN if baseline was normal; >20.0 x baseline if baseline was abnormal	-
Alkaline phosphatase increased	>ULN - 2.5 x ULN if baseline was normal; 2.0 - 2.5 x baseline if baseline was abnormal	>2.5 - 5.0 x ULN if baseline was normal; >2.5 - 5.0 x baseline if baseline was abnormal	>5.0 - 20.0 x ULN if baseline was normal; >5.0 - 20.0 x baseline if baseline was abnormal	>20.0 x ULN if baseline was normal; >20.0 x baseline if baseline was abnormal	-
Aspartate aminotransferase increased	>ULN - 3.0 x ULN if baseline was normal; 1.5 - 3.0 x baseline if baseline was abnormal	>3.0 - 5.0 x ULN if baseline was normal; >3.0 - 5.0 x baseline if baseline was abnormal	>5.0 - 20.0 x ULN if baseline was normal; >5.0 - 20.0 x baseline if baseline was abnormal	>20.0 x ULN if baseline was normal; >20.0 x baseline if baseline was abnormal	-
Blood bicarbonate decreased	<LLN and no intervention initiated	-	-	-	-
Blood bilirubin increased	>ULN - 1.5 x ULN if baseline was normal; > 1.0 - 1.5 x baseline if baseline was abnormal	>1.5 - 3.0 x ULN if baseline was normal; >1.5 - 3.0 x baseline if baseline was abnormal	>3.0 - 10.0 x ULN if baseline was normal; >3.0 - 10.0 x baseline if baseline was abnormal	>10.0 x ULN if baseline was normal; >10.0 x baseline if baseline was abnormal	-
Cholesterol high	>ULN - 300 mg/dL; >ULN - 7.75 mmol/L	>300 - 400 mg/dL; >7.75 - 10.34 mmol/L	>400 - 500 mg/dL; >10.34 - 12.92 mmol/L	>500 mg/dL; >12.92 mmol/L	-
CPK increased	>ULN - 2.5 x ULN	>2.5 x ULN - 5 x ULN	>5 x ULN - 10 x ULN	>10 x ULN	-
Creatinine increased	>ULN - 1.5 x ULN	>1.5 - 3.0 x baseline; >1.5 - 3.0 x ULN	>3.0 x baseline; >3.0 - 6.0 x ULN	>6.0 x ULN	-

CTCAE 5.0	CTCAE Grade				

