CTCAE Term	Grade 1	Grade 2	Grade 3	Grade 4	Grade 5
GGT increased	>ULN - 2.5 x ULN if baseline was normal; 2.0 - 2.5 x baseline if baseline was abnormal	>2.5 - 5.0 x ULN if baseline was normal; >2.5 - 5.0 x baseline if baseline was abnormal	>5.0 - 20.0 x ULN if baseline was normal; >5.0 - 20.0 x baseline if baseline was abnormal	>20.0 x ULN if baseline was normal; >20.0 x baseline if baseline was abnormal	-
Haptoglobin decreased	<LLN	-	-	-	-
Hemoglobin increased	Increase in >0 - 2 g/dL	Increase in >2 - 4 g/dL	Increase in >4 g/dL	-	-
INR increased	>1.2 - 1.5; >1 - 1.5 x baseline if on anticoagulation; monitoring only indicated	>1.5 - 2.5; >1.5 - 2.5 x baseline if on anticoagulation; dose adjustment indicated	>2.5; >2.5 x baseline if on anticoagulation; bleeding	-	-
Lipase increased	>ULN - 1.5 x ULN	>1.5 - 2.0 x ULN; >2.0 - 5.0 x ULN and asymptomatic	>2.0 - 5.0 x ULN with signs or symptoms; >5.0 x ULN and asymptomatic	>5.0 x ULN and with signs or symptoms	-
Lymphocyte count decreased	<LLN - 800/mm ³ ; <LLN - 0.8 x 10 ⁹ /L	<800 - 500/mm ³ ; <0.8 - 0.5 x 10 ⁹ /L	<500 - 200/mm ³ ; <0.5 - 0.2 x 10 ⁹ /L	<200/mm ³ ; <0.2 x 10 ⁹ /L	-
Lymphocyte count increased	-	>4000/mm ³ - 20,000/mm ³	>20,000/mm ³	-	-
Neutrophil count decreased	<LLN - 1500/mm ³ ; <LLN - 1.5 x 10 ⁹ /L	<1500 - 1000/mm ³ ; <1.5 - 1.0 x 10 ⁹ /L	<1000 - 500/mm ³ ; <1.0 - 0.5 x 10 ⁹ /L	<500/mm ³ ; <0.5 x 10 ⁹ /L	-
Platelet count decreased	<LLN - 75,000/mm ³ ; <LLN - 75.0 x 10 ⁹ /L	<75,000 - 50,000/mm ³ ; <75.0 - 50.0 x 10 ⁹ /L	<50,000 - 25,000/mm ³ ; <50.0 - 25.0 x 10 ⁹ /L	<25,000/mm ³ ; <25.0 x 10 ⁹ /L	-
Serum amylase increased	>ULN - 1.5 x ULN	>1.5 - 2.0 x ULN; >2.0 - 5.0 x ULN and asymptomatic	>2.0 - 5.0 x ULN with signs or symptoms; >5.0 x ULN and asymptomatic	>5.0 x ULN and with signs or symptoms	-
White blood cell decreased	<LLN - 3000/mm ³ ; <LLN - 3.0 x 10 ⁹ /L	<3000 - 2000/mm ³ ; <3.0 - 2.0 x 10 ⁹ /L	<2000 - 1000/mm ³ ; <2.0 - 1.0 x 10 ⁹ /L	<1000/mm ³ ; <1.0 x 10 ⁹ /L	-
Hypercalcemia	Corrected serum calcium of >ULN - 11.5 mg/dL; >ULN - 2.9 mmol/L; Ionized calcium >ULN - 1.5 mmol/L	Corrected serum calcium of >11.5 - 12.5 mg/dL; >2.9 - 3.1 mmol/L; Ionized calcium >1.5 - 1.6 mmol/L; symptomatic	Corrected serum calcium of >12.5 - 13.5 mg/dL; >3.1 - 3.4 mmol/L; Ionized calcium >1.6 - 1.8 mmol/L; hospitalization indicated	Corrected serum calcium of >13.5 mg/dL; >3.4 mmol/L; Ionized calcium >1.8 mmol/L; life-threatening consequences	Death

CTCAE 5.0		CTCAE Grade				

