CTCAE Term	Grade 1	Grade 2	Grade 3	Grade 4	Grade 5	
Hyperkalemia	>ULN - 5.5 mmol/L	>5.5 - 6.0 mmol/L; intervention initiated	>6.0 - 7.0 mmol/L; hospitalization indicated	>7.0 mmol/L; life-threatening consequences	Death	
Hypermagnesemia	>ULN - 3.0 mg/dL; >ULN - 1.23 mmol/L	-	>3.0 - 8.0 mg/dL; >1.23 - 3.30 mmol/L	>8.0 mg/dL; >3.30 mmol/L; life-threatening consequences	Death	
Hypernatremia	>ULN - 150 mmol/L	>150 - 155 mmol/L; intervention initiated	>155 - 160 mmol/L; hospitalization indicated	>160 mmol/L; life-threatening consequences	Death	
Hypertriglyceridemia	150 mg/dL - 300 mg/dL; 1.71 mmol/L - 3.42 mmol/L	>300 mg/dL - 500 mg/dL; >3.42 mmol/L - 5.7 mmol/L	>500 mg/dL - 1000 mg/dL; >5.7 mmol/L - 11.4 mmol/L	>1000 mg/dL; >11.4 mmol/L; life-threatening consequences	Death	
Hyperuricemia	>ULN without physiologic consequences	-	>ULN with physiologic consequences	Life-threatening consequences	Death	
Hypoalbuminemia	<LLN - 3 g/dL; <LLN - 30 g/L	<3 - 2 g/dL; <30 - 20 g/L	<2 g/dL; <20 g/L	Life-threatening consequences; urgent intervention indicated	Death	
Hypocalcemia	Corrected serum calcium of <LLN - 8.0 mg/dL; <LLN - 2.0 mmol/L; Ionized calcium <LLN - 1.0 mmol/L	Corrected serum calcium of <8.0 - 7.0 mg/dL; <2.0 - 1.75 mmol/L; Ionized calcium <1.0 - 0.9 mmol/L; symptomatic	Corrected serum calcium of <7.0 - 6.0 mg/dL; <1.75 - 1.5 mmol/L; Ionized calcium <0.9 - 0.8 mmol/L; hospitalization indicated	Corrected serum calcium of <6.0 mg/dL; <1.5 mmol/L; Ionized calcium <0.8 mmol/L; life-threatening consequences	Death	
Hypoglycemia	<LLN - 55 mg/dL; <LLN - 3.0 mmol/L	<55 - 40 mg/dL; <3.0 - 2.2 mmol/L	<40 - 30 mg/dL; <2.2 - 1.7 mmol/L	<30 mg/dL; <1.7 mmol/L; life-threatening consequences; seizures	Death	
Hypokalemia	<LLN - 3.0 mmol/L	Symptomatic with <LLN - 3.0 mmol/L; intervention indicated	<3.0 - 2.5 mmol/L; hospitalization indicated	<2.5 mmol/L; life-threatening consequences	Death	
Hypomagnesemia	<LLN - 1.2 mg/dL; <LLN - 0.5 mmol/L	<1.2 - 0.9 mg/dL; <0.5 - 0.4 mmol/L	<0.9 - 0.7 mg/dL; <0.4 - 0.3 mmol/L	<0.7 mg/dL; <0.3 mmol/L; life-threatening consequences	Death	
Hyponatremia	<LLN - 130 mmol/L	125-129 mmol/L and asymptomatic	125-129 mmol/L symptomatic; 120-124 mmol/L regardless of symptoms	<120 mmol/L; life-threatening consequences	Death	

* Since anticoagulation medication is NOT captured in lab data, the condition for anticoagulation medication is ignored in the grade derivation.

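### SAP Appendix 2 sets aside its own INR criteria for anticoagulated subjects although the medication eCRF can identify them; for any such subject, a small rise across 2.5 is tabulated as treatment-emergent Grade 3.

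*SAP*

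**What the plan says.** The INR row of SAP Appendix 2 has two sets of cut-offs. The absolute set is above 1.2 to 1.5 (Grade 1), above 1.5 to 2.5 (Grade 2) and above 2.5 (Grade 3, the highest printed). The second set uses the same 1.5 and 2.5 as multiples of baseline, with Grade 1 starting above 1; its Grade 1 entry ends "x baseline if on anticoagulation; monitoring only indicated". The footnote removes the second set: "Since anticoagulation medication is NOT captured in lab data, the condition for anticoagulation medication is ignored in the grade derivation". INR is the only row of the appendix with an anticoagulation condition.

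Other parts of the plan bear on this:

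- **Eligibility.** Protocol 4.2 limits screening INR to 1.4, "unless due to therapeutic anticoagulation". Protocol 4.3 excludes MELD above 12, "unless due to an alternate etiology such as therapeutic anticoagulation", and treats the Child-Pugh limit similarly.
- **Data collected.** Protocol 5.4: "Concomitant medications taken within 28 days of screening through the follow-up visit need to be recorded" in source documents and the eCRF. SAP 5.2 derives UDCA use from the concomitant medication page.
- **Status used elsewhere.** SAP 7.2.3 applies two INR criteria (above 1.5, with raised ALT/AST) only to subjects not on anticoagulation.
- **Outputs.** SAP 7.2.2.1 calls a result treatment-emergent when it rises at least one grade from baseline. SAP 7.2.2.2 tabulates the worst grade and lists treatment-emergent Grade 3 or 4 results. SAP 7.2.1 provides no descriptive laboratory statistics. SAP 7.4 neither summarizes nor lists medications.

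**The concern.** The footnote's reason is true of the laboratory file but not of the trial database. One SAP section treats anticoagulation status as unavailable, while another cannot be programmed without it.

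Laboratory tests are part of the primary safety endpoint (Protocol 8.1.2). With descriptive statistics dropped, the graded table is the main planned summary of INR. In that table, a Grade 3 that reflects anticoagulation looks the same as one that might reflect the drug or worsening liver function. The rule can also err the other way: a subject who already starts at the top grade contributes no treatment-emergent event, however far INR rises.

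**Working it through.** **Inputs.** The cut-offs are from the INR row of SAP Appendix 2, and the treatment-emergent rule is from SAP 7.2.2.1. Baseline is the last value on or before first dose (SAP 3.7.3; INR is not among the averaged liver tests). The INR pairs below are assumed illustrations, since the documents give no INR data. The plan states no figure to reproduce.

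**Step 1: grade each pair both ways.** Ratio = later INR / baseline INR. The last column reads the multiples as replacing the absolute cut-offs.

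| Baseline | Later | Ratio | Absolute grade (footnote) | Treatment-emergent under footnote | Multiple-of-baseline grade |
|---|---|---|---|---|---|
| 2.4 | 2.6 | 1.08 | 2 to 3 | yes, Grade 3 | 0 to 1 |
| 2.0 | 2.6 | 1.30 | 2 to 3 | yes, Grade 3 | 0 to 1 |
| 1.7 | 2.6 | 1.53 | 2 to 3 | yes, Grade 3 | 0 to 2 |
| 1.6 | 2.5 | 1.56 | 2 to 2 | no | 0 to 2 |
| 2.6 | 2.8 | 1.08 | 3 to 3 | no | 0 to 1 |
| 2.6 | 6.6 | 2.54 | 3 to 3 | no | 0 to 3 |

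The first three rows remain treatment-emergent on the multiple scale, but at Grade 1 or 2 and so outside the Grade 3/4 listing. The last row is a large rise that the footnote rule cannot count.

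**Step 2: does the result depend on how the two sets combine?** The INR row separates them by semicolons. The ALT row, by contrast, makes its sets exclusive, for example "1.5 - 3.0 x baseline if baseline was abnormal". Suppose the INR sets are alternatives and the worse grade applies. For any baseline b of 1.0 or more, x/b is at most x, so a value above 1.5 or 2.5 times baseline is already above 1.5 or 2.5. The multiples could then add only a Grade 1. On a grid of baselines 1.0 to 6.0 and values 0.8 to 12.0 in steps of 0.1, they change the grade in three cells: 1.0 to 1.1, 1.0 to 1.2 and 1.1 to 1.2. That reading leaves the anticoagulation text almost without function, so replacement is the reading that gives it meaning. The documents do not state it outright.

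**Step 3: can a reader recognize such a subject?** "The MELD score will be calculated by using the following formula" introduces the formula in Protocol 6.8.5. With bilirubin and creatinine at their floor of 1.0, MELD = 10 x (1.12 ln INR + 0.643):

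- INR 2.0: 10 x (1.12 x 0.693 + 0.643) = 14.2
- INR 2.5: 10 x (1.12 x 0.916 + 0.643) = 16.7
- INR 1.4: 10 x (1.12 x 0.336 + 0.643) = 10.2

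Entry at INR 2.0 to 2.5 breaches both the INR and the MELD limit unless an exception applies. SAP 4.3 says "A by-subject listing will be provided for those subjects who did not meet at least 1 eligibility (inclusion or exclusion) criterion". A subject with a high screening INR who is absent from that listing therefore probably qualified through the exception. This inference fails for a subject who entered on an anticoagulant with INR 1.4 or less, and for one who started after baseline.

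**Step 4: size.** One subject is 1/20 = 5 percentage points at the planned number. SAP 1 says enrollment ended early; at an assumed 10 subjects it is 1/10 = 10 points.

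**Step 5: can the frequency be estimated?** I simulated an anticoagulated subject with no drug effect, INR SD 0.2 to 0.4 and 4 or 5 post-baseline values (all assumed). Treatment-emergent Grade 3 under the footnote rule occurs in 1.2% to 58% if mean INR is 2.0 to 2.5, in 0.03% to 14% if it is 1.8, and in 1.2% to 13% if it is 3.0. The answer depends on where the assumed mean sits relative to 2.5, so these figures do not estimate anything in this trial.

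**The case against.** The strongest reply has four parts.

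- **It may concern nobody.** No text reports an anticoagulated subject. Protocol 4.3 excludes hypercoagulable conditions and thromboembolic disease, although controlled atrial fibrillation is allowed, and enrollment stopped early. This stands: the point is conditional and any number is probably small.
- **The row may mean that either set suffices.** Then 2.6 is Grade 3 with or without the footnote. The text cannot rule this out, but Step 2 shows that it would make the printed criteria nearly empty. The missing marker and the conflict with SAP 7.2.3 remain on either reading.
- **The data remain visible.** SAP 7.2 lists all coagulation results by subject with abnormal values flagged, and the Grade 3/4 listing shows every INR result for the subject concerned. Under Protocol 7.1.3, laboratory changes that need intervention or lead to interruption, modification or discontinuation of study drug are recorded as AEs, and those reach the tables in SAP 7.1.6. This stands and is the main reason the point is minor. These outputs show the values but are not designed to show the anticoagulant.
- **Absolute grading is a disclosed convention, and the other scale has a cost.** Any rise above baseline is Grade 1 on the multiple scale, so stable anticoagulated subjects would often carry a mark. This stands, and is why both grades should be shown rather than one substituted for the other.

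A reader might infer that anticoagulation is flagged nowhere. The documents do not support that: SAP Appendix 3 (programming specifications) is not in the supplied text, and SAP 7.2.3 implies that the status is derived somewhere.

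**Conclusion.** The point holds as a minor one. The footnote drops printed criteria for a reason that the SAP's own use of the medication page and SAP 7.2.3 contradict. For any anticoagulated subject, it can turn a rise of about 8% in INR into a treatment-emergent Grade 3, and it prevents a baseline above 2.5 from ever yielding a treatment-emergent result. The size is one subject at a time, 5 percentage points each at 20 subjects.

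This rests on two assumptions: that at least one such subject was enrolled or started an anticoagulant on study, and that the multiples replace the absolute cut-offs. If nobody was anticoagulated, nothing changes.

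A reader might go further and infer that a large share of INR Grade 3 events will be spurious, or that an INR signal will be concealed. Neither follows. The documents give no INR distribution and no count of anticoagulated subjects, and the raw values and related AEs are still reported.

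**What to change.** Replace the Appendix 2 footnote with a rule that:

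1. derives an anticoagulant flag from the concomitant-medication eCRF, matched in time to each INR sample so that a start after baseline is caught;
2. marks flagged subjects in the INR abnormality table and in the Grade 3/4 listing;
3. shows their multiple-of-baseline grade beside the absolute grade;
4. uses the same flag for the INR criteria in SAP 7.2.3.

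Record the change in SAP 2.3, because Protocol 8.5.3 assigns grading for analysis to the central laboratory. Showing both grades avoids having to settle which set governs.

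The cost is one merge of data already collected, one rule and one entry in SAP 2.3. The downside is more Grade 1 marks in flagged subjects on the multiple scale. No output changes if nobody is flagged.
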